#### Assessment of Intensity

- The investigator will make an assessment of intensity for each AE and SAE reported during the study and assign it to 1 of the following categories:
  - Mild: An event that is easily tolerated by the participant, causing minimal discomfort and not interfering with everyday activities.
  - Moderate: An event that causes sufficient discomfort and interferes with normal everyday activities.
  - Severe: An event that prevents normal everyday activities. An AE that is assessed as severe should not be confused with an SAE. Severe is a category utilized for rating the intensity of an event; and both AEs and SAEs can be assessed as severe.
  - An event is defined as 'serious' when it meets at least 1 of the predefined outcomes as described in the definition of an SAE, NOT when it is rated as severe.
-

### Assessment of Causality

- The investigator is obligated to assess the relationship between study intervention and each occurrence of each AE/SAE.
- A “reasonable possibility” of a relationship conveys that there are facts, evidence, and/or arguments to suggest a causal relationship, rather than a relationship cannot be ruled out.
- The investigator will use clinical judgment to determine the relationship.
- Alternative causes, such as underlying disease(s), concomitant therapy, and other risk factors, as well as the temporal relationship of the event to study intervention administration will be considered and investigated.
- The investigator will also consult the Investigator’s Brochure (IB) and/or Product Information, for marketed products, in his/her assessment.
- For each AE/SAE, the investigator **must** document in the medical notes that he/she has reviewed the AE/SAE and has provided an assessment of causality.
- There may be situations in which an SAE has occurred and the investigator has minimal information to include in the initial report to. However, **it is very important that the investigator always make an assessment of causality for every event before the initial transmission** of the SAE data.
- The investigator may change his/her opinion of causality in light of follow-up information and send an SAE follow-up report with the updated causality assessment.
- The causality assessment is one of the criteria used when determining regulatory reporting requirements.

### Follow-up of AEs and SAEs

- The investigator is obligated to perform or arrange for the conduct of supplemental measurements and/or evaluations as medically indicated or as requested to elucidate the nature and/or causality of the AE or SAE as fully as possible. This may include additional laboratory tests or investigations, histopathological examinations, or consultation with other health care professionals.
- New or updated information will be recorded in the originally completed CRF.
- The investigator will submit any updated SAE data to sponsor contact within 24 hours of receipt of the information.

#### 9.5.4 Time Period and Frequency for Collecting AE and SAE Information

All SAEs will be collected from the signing of the informed consent form (ICF) OR until the follow-up visit at the time points specified in the SoA.

All AE will be collected from the signing of the ICF until at the time points specified in the SoA .

Medical occurrences that begin before the start of study intervention but after obtaining informed consent will be recorded on the Medical History/Current Medical Conditions section of the case report form (CRF) not the AE section.

All SAEs will be recorded and reported to the sponsor or designee immediately and under no circumstances should this exceed 24 hours. The investigator will submit any updated SAE data to the sponsor within 24 hours of it being available.

Investigators are not obligated to actively seek AE or SAE after conclusion of the study participation. However, if the investigator learns of any SAE, including a death, at any time after a participant has been discharged from the study, and he/she considers the event to be reasonably related to the study intervention or study participation, the investigator must promptly notify the sponsor.

### 9.5.5 Follow-up of AEs and SAEs

After the initial AE/SAE report, the investigator is required to proactively follow each participant at subsequent visits/contacts. All SAEs, and non-serious AEs will be followed until resolution, stabilization, the event is otherwise explained, or the participant is lost to follow-up.

### 9.5.6 Regulatory Reporting Requirements for SAEs

- Prompt notification by the investigator to the sponsor of an SAE is essential so that legal obligations and ethical responsibilities towards the safety of participants and the safety of a study intervention under clinical investigation are met. See section [9.5.4](#) for reporting time periods. Investigator should notify the sponsor by sending the completed SAE forms to:

PPD [redacted] or Fax: PPD [redacted]

- The sponsor has a legal responsibility to notify both the local regulatory authority and other regulatory agencies about the safety of a study intervention under clinical investigation. The sponsor will comply with country-specific regulatory requirements relating to safety reporting to the regulatory authority, Institutional Review Boards (IRB)/Independent Ethics Committees (IEC), and investigators, as applicable.
- Investigator safety reports must be prepared for suspected unexpected serious adverse reactions (SUSAR) according to local regulatory requirements and sponsor policy and forwarded to investigators as necessary.
- An investigator who receives an investigator safety report describing an SAE or other specific safety information (eg, summary or listing of SAEs) from the sponsor will review and then file it along with the Investigational Product information and will notify the IRB/IEC, if appropriate according to local requirements.

### 9.5.7 Pregnancy

The investigator must report to the sponsor any pregnancy occurring in a female study participant during her participation in this study. The outcome of the pregnancy should be followed up carefully, and any outcome of the mother and the child at delivery should be reported.

For all reports, the forms provided are to be used. The investigator should submit them within the same timelines as an SAE. Send the completed SAE forms to:

PPD

or Fax:

PPD

### **9.5.8 Disease-Related Events and/or Disease-Related Outcomes Not Qualifying as AEs or SAEs**

The following events are common in participants with upper respiratory allergies

- Runny nose
- Sneezing
- Itchy, watery eyes
- Itching of the nose or throat
- Nasal congestion

Although the study drug contains an active ingredient approved for all the above listed symptoms (except nasal congestion), onset of relief of symptoms may or may not be achieved prior to the conclusion of the study assessment. Given that this study is not designed to assess efficacy and because these events are typically associated with the condition under study, they do not qualify as an AE.

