#### **Visit 1 (Day 1)**

- One test product will be provided in a dosing cup to each participant who will then be asked to completely chew completely before swallowing. Participants cannot drink water until end of visit.
- Study staff initiates timer as soon as the study medication is administered
- Participant will be asked to indicate on the case report form (CRF) if he/she perceives a cooling sensation in the mouth, nose and throat at 10 seconds, 30 seconds and 1 minutes post ingestion of test product
- After the 1-minute time point, participants will be asked to complete a brief questionnaire on the sensory attributes of the test product. Participants will be allowed four (4) minutes to complete the questionnaire.
- Following the completion of the questionnaire, participants will continue to evaluate perception of cooling sensation in the mouth, nose and throat at 5 minute intervals, starting at the 5 minute time point for 60 minutes
- Following completion of all study assessments, participants will be asked open ended questions which will be used for learning purposes
- Adverse events, if applicable, will be recorded
- Participants will be reminded to report any unusual or unexpected medical changes within the 24 hour period following administration of the study medication to site personnel

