### **9.3.2 Medical History**

Medical history findings (i.e. previous diagnoses, diseases or surgeries) meeting all criteria listed below will be collected as available to the investigator:

- Start before signing of the informed consent
- Considered relevant for the participant's study eligibility.

Detailed instructions on the differentiation between (i) medical history and (ii) adverse events can be found in Section 9.5.1.

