#### Events Meeting the AE Definition

- Any abnormal laboratory test results (hematology, clinical chemistry, or urinalysis) or other safety assessments (eg, ECG, radiological scans, vital signs measurements), including those that worsen from baseline, considered clinically significant in the medical and scientific judgment of the investigator.
- Exacerbation of a chronic or intermittent pre-existing condition including either an increase in frequency and/or intensity of the condition.
- New conditions detected or diagnosed after study intervention administration even though it may have been present before the start of the study.
- Signs, symptoms, or the clinical sequelae of a suspected drug-drug interaction.
- Signs, symptoms, or the clinical sequelae of a suspected overdose of either study intervention or a concomitant medication. Overdose per se will not be reported as an AE/SAE unless it is an intentional overdose taken with possible suicidal/self-harming intent. Such overdoses should be reported regardless of sequelae.
- The signs, symptoms, and/or clinical sequelae resulting from lack of efficacy will be reported as AE or SAE if they fulfil the definition of an AE or SAE. Also, “lack of efficacy” or “failure of expected pharmacological action” also constitutes an AE or SAE.

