#### Events NOT Meeting the AE Definition

- Any clinically significant abnormal laboratory findings or other abnormal safety assessments which are associated with the underlying disease, unless judged by the investigator to be more severe than expected for the participant’s condition.
- The disease/disorder being studied or expected progression, signs, or symptoms of the disease/disorder being studied, unless more severe than expected for the participant’s condition.

- 
- Medical or surgical procedure (eg, endoscopy, appendectomy): the condition that leads to the procedure is the AE.
  - Situations in which an untoward medical occurrence did not occur (social and/or convenience admission to a hospital).
  - Anticipated day-to-day fluctuations of pre-existing disease(s) or condition(s) present or detected at the start of the study that do not worsen.
- 

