### 9.5.3 Recording and Follow-Up of AE and/or SAE

#### AE and SAE Recording

- When an AE/SAE occurs, it is the responsibility of the investigator to review all documentation (eg, hospital progress notes, laboratory reports, and diagnostics reports) related to the event.
- The investigator will then record all relevant AE/SAE information in the CRF.
- It is not acceptable for the investigator to send photocopies of the participant's medical records in lieu of completion of the AE/SAE CRF page.
- There may be instances when copies of medical records for certain cases are requested. In this case, all participant identifiers, with the exception of the participant number, will be redacted on the copies of the medical records before submission.
- The investigator will attempt to establish a diagnosis of the event based on signs, symptoms, and/or other clinical information. Whenever possible, the diagnosis (not the individual signs/symptoms) will be documented as the AE/SAE.

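### Section 9.5.8 exempts five allergy symptoms from AE status without the limits on worsening and unexpected severity that Section 9.5.1 sets

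*Combined protocol and SAP*

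**What the plan says.** Section 9.5.8 names five symptoms as common in people with upper respiratory allergies: runny nose, sneezing, itchy or watery eyes, itching of the nose or throat, and nasal congestion. It notes that "onset of relief of symptoms may or may not be achieved prior to the conclusion of the study assessment" and that the study does not assess efficacy. It then concludes that, "because these events are typically associated with the condition under study, they do not qualify as an AE".

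Section 9.5.1 deals with the same ground in two lists. Among events that are AEs it places "Exacerbation of a chronic or intermittent pre-existing condition including either an increase in frequency and/or intensity of the condition". Among events that are not AEs it places "symptoms of the disease/disorder being studied, unless more severe than expected" for the participant's condition. That second list also exempts day-to-day fluctuations of a pre-existing condition, but only where there is no worsening.

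The one pointer between sections is in 9.3.2: "Detailed instructions on the differentiation between (i) medical history and (ii) adverse events can be found in Section 9.5.1". It concerns the boundary between medical history and AEs. It does not say whether 9.5.1 or 9.5.8 decides the status of a listed symptom.

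**The concern.** The exclusion sentence in 9.5.8 has no condition attached, whereas 9.5.1 attaches two. A listed symptom that becomes more frequent or more intense after dosing, or is unexpectedly severe, can therefore be an AE under one section and not under the other.

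AE status decides what happens next. Section 9.5.3 states that "The investigator is obligated to assess the relationship between study intervention and each occurrence of each AE/SAE", and it requires an intensity grade. Section 9.5.5 requires follow-up to resolution or stabilization. Section 9.2.4 provides contact in the following week for an ongoing AE, and the safety population in Section 10.2 is defined for the analysis of AEs. A symptom that is not classed as an AE falls outside all of these. Four sites applying different readings would produce AE counts that are not comparable, and some events possibly caused by the tablet might never be assessed for causality.

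**Working it through.** No figure in the plan can be reproduced for this point. The check is a comparison of texts, followed by a scale calculation on an assumed rate.

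**Step 1: the rules side by side**

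| Post-dose event in a listed symptom | Section 9.5.1 | Section 9.5.8, read literally |
|---|---|---|
| Persists unchanged | Not an AE | Not an AE |
| Increases in frequency or intensity | AE under the exacerbation item | Not an AE |
| More severe than expected for that participant | Exemption does not apply | Not an AE |

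The sections agree on the first row and part company on the other two.

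**Step 2: could 9.5.8 be confined to symptoms that are merely unrelieved?** Its rationale, that relief may not come in time, suggests so. Other parts of the protocol do not fit that reading:

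- Inclusion criterion 4 (Section 6.1) admits asymptomatic participants. For them, a listed symptom after dosing is new, not unrelieved.
- Exclusion criterion 5 (Section 6.2) removes anyone with congestion at the visit. Congestion after dosing would normally be new, yet it is on the exempt list.
- Section 9.5.8 itself says the active ingredient is not approved for nasal congestion, so waiting for relief cannot be the reason for exempting that item.
- Section 9.5.1 treats lack of efficacy as an AE or SAE, while 9.5.8 uses possible non-relief as part of its reason for exemption.
- The heading of 9.5.8 covers both AEs and SAEs, but its text speaks only of AEs.

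**Step 3: scale.** Inputs: about 400 participants completing, 100 at each of 4 sites (Section 5.1). The rate r of a worsened or unexpectedly severe listed symptom in the 24 hours after the dose is not in the documents. It is assumed to lie between 0.5% and 5%.

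- Study-wide events = 400 × r
- Events per site = 100 × r
- Events unrecorded if k sites read 9.5.8 literally = k × 100 × r

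| r (assumed) | Study-wide | Per site | Unrecorded, k = 2 | Unrecorded, k = 4 |
|---|---|---|---|---|
| 0.5% | 2 | 0.5 | 1 | 2 |
| 1% | 4 | 1 | 2 | 4 |
| 2% | 8 | 2 | 4 | 8 |
| 5% | 20 | 5 | 10 | 20 |

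The 400 are completers. Dropouts are replaced (Section 6.5), so the number dosed, which is the base for the AE analysis, may be slightly higher.

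**The case against.** The best defence is that 9.5.8 simply names, for this study, the disease symptoms that 9.5.1 already exempts, and so inherits the severity limit of that exemption. On that view only a cross-reference is missing. The reading is reasonable and some sites would adopt it. But the exclusion sentence does not say so, and the points in Step 2 show that the list reaches new symptoms as well as persisting ones. A site that took 9.5.8 at its word would not be misreading it.

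A second objection is that 9.5.1 is not one clean rule. Its exacerbation item covers pre-existing conditions generally, while its exemption for the studied disease extends to expected progression, so a modest increase in sneezing is arguable within 9.5.1 alone. This stands in part: the clearest conflict is the symptom that is more severe than expected. Still, the worsening limit appears in both lists of 9.5.1, since the fluctuation item also excludes worsening. Section 9.5.8 drops both limits.

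A third objection is that the consequences are slight and the rate is a guess. Both are true. This is a single dose of an approved product in a one-arm sensory study with no planned AE comparison. Participants are reminded to "report any unusual or unexpected medical changes within the 24 hour period" after dosing, so an event may reach the site, although its classification stays open. A diagnosed reaction can still be entered, because "the diagnosis (not the individual signs/symptoms) will be documented as the AE/SAE" whenever possible. The gap is therefore mainly in isolated, non-serious symptoms. The calculation also presumes that every such event comes to the site's attention.

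**Conclusion.** The concern holds, as a minor one. Section 9.5.8 as written conflicts with 9.5.1 on listed symptoms that worsen or exceed expected severity, and nothing in the documents settles which applies. Followed literally, it keeps such events out of the AE record, the causality assessment and the AE analysis.

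On the assumed rates the effect is 2 to 20 records across the study, and fewer if only some sites take the literal reading. The textual conflict does not depend on those rates; only its size does. That sites would actually differ is a possibility, not something the documents show. The primary variable, agreement on cooling sensation, is unaffected.

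**What to change.** Add one sentence to 9.5.8 stating that the listed symptoms are exempt only within the limits of 9.5.1: the exemption does not apply when a symptom increases in frequency or intensity, or when it exceeds the severity expected for that participant. Because 9.5.1 sets out these limits in separate items, the sponsor should check that the new sentence and both 9.5.1 lists read as one rule.

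The sentence applies limits already in the protocol and needs no new form, visit or assessment. The cost is a short text change and probably a few more non-serious AE records.

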## **10. STATISTICAL METHODS AND DETERMINATION OF SAMPLE SIZE**

### **10.1 General Considerations**

All statistical analyses will be conducted using SAS. Missing data will not be imputed.

### **10.2 Analysis Sets**

All participants who have an evaluation data for study medication will be included into the statistical analysis of the primary parameter.

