## 5. STUDY DESIGN

### 5.1 Design Overview

This study is an open label (participants blinded to brand), multi-center study assessing the sensory attributes of a flavored antihistamine chewable tablet.

The study will consist of one site visit where a single dose of study product will be administered.

Approximately 520 subjects will be screened across 4 sites in the North East, South, Midwest and West regions within the United States of America. With approximately 400 adults completing; 100 per location.

**Visit 1:** participants will present for an onsite screening for inclusion and exclusion criteria prior to the beginning of any product evaluation. Upon qualification and prior to participation in the study, participants will sign an informed consent form.

Qualifying participants will be instructed to chew completely before swallowing, one full dose (10 mg loratadine chewable tablet) during this visit. The study visit will last approximately 60-75 minutes.

A detailed description of study procedures and tabular schedule of evaluations will be found in [Section 9](#).

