**9.4.2 Sensory Attributes Questionnaire**

Participants will be instructed to complete the questionnaire as following:

“Please indicate to what level you agree or disagree with the corresponding statement:”

Question	Strongly agree (5)	Somewhat agree (4)	Neither agree nor disagree (3)	Somewhat disagree (2)	Strongly disagree (1)
The product provides a cooling sensation					
The product provides a cooling sensation in the mouth					
The product provides a cooling sensation in the nose					
The product provides a cooling sensation in the throat					
The product provides a refreshing sensation					
The product provides a refreshing sensation in the mouth					
The product provides a refreshing sensation in the nose					
The product provides a refreshing sensation in the throat					
The product tastes great					
The product experience was enjoyable					

I like the flavor sensation of the product					
The product feels soothing on the throat					
The sensory experience is unique for an allergy medicine					
The cooling sensation is refreshing					

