#### **Safety Population**

Any participant who receives the study medication will be included for the analyses of adverse events.

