#### **Statistical and Analytical Plans**

**Questionnaire:** The primary variable of interest will be analyzed by determining the percentage of selection of the top 2 choices (strongly agree and somewhat agree). This percentage and its 95% confidence interval will be calculated, if the lower bound of the confidence interval is greater than 50%, the statistical majority of agreement will be claimed. Other secondary variables of interests from the questionnaire will be analyzed in the same manner as the primary variable.

**Time to perception of cooling and duration of cooling:** These secondary variables will be analyzed descriptively (Mean, Standard deviation, Median, Mode and Range). The mean time point at which cooling is initially perceived will be claimed as the onset of cooling. The mean time point at which cooling is perceived to last will be claimed as the duration of cooling.

Participants who never reach “Yes” in the perception of cooling will be (1) imputed by the maximum study time (60 minutes), and (2) treated as censored and used Kaplan-Meyer to estimate the median time to perception of cooling.

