### 11.5 Missing Data

Any missing data will be left as such.

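### Does the undefined evaluation-data condition in section 10.2 put the majority-of-agreement claim at risk by leaving out dosed participants who never answered?

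*Combined protocol and SAP*

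**What the plan says.** The primary variable is top-two-box agreement (strongly or somewhat agree) on the cooling item of a 14-item questionnaire. Section 10.3 claims a majority if the lower 95% confidence bound exceeds 50%, and adds: "Other secondary variables of interests from the questionnaire will be analyzed in the same manner as the primary variable". It names no interval method.

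The analysis set in 10.2 is: "All participants who have an evaluation data for study medication will be included into the statistical analysis of the primary parameter". The only set that takes in everyone dosed is for safety: "Any participant who receives the study medication will be included for the analyses of adverse events".

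On missing values, 10.1 states "Missing data will not be imputed" and 11.5 states "Any missing data will be left as such".

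On timing, the Visit 1 description in 9.2.4 has cooling entries at 10 seconds, 30 seconds and 1 minute, and then: "After the 1-minute time point, participants will be asked to complete a brief questionnaire on the sensory attributes of the test product". Four minutes are allowed. Section 7.6 has a team member watch and document the dosing.

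On losses, 6.4.1 defines a dropout as someone already dosed, 6.5 replaces dropouts, and 5.1 sets the target: "With approximately 400 adults completing; 100 per location".

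**The concern.** The visit yields two kinds of evaluation, the timed cooling entries and the questionnaire, and the first begins before the second. A participant who takes the tablet, records cooling at 10 seconds and then leaves has some evaluation data but no primary response. Taken alone, 10.2 seems to admit that person, while 10.1 and 11.5 supply no value to analyse. An open-label study with one decision rule should not leave its denominator to be settled after the data are seen.

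Replacement adds to the worry. About 400 can complete however many dosed people were lost first, and the plan requires details for screen failures but no count or reasons for dosed participants without an answer.

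At stake is whom the claim describes: those who answered, or all who took the tablet. If people who dislike the product are the ones who stop, the percentage is too high. That is plausible for liking items and for statements such as "The product feels soothing on the throat", which face the same 50% rule. For the cooling item the direction is unclear, since someone who stops because the sensation is too strong may still agree that the product cools.

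**Working it through.** **Step 1: what the text fixes.** The statistic in 10.3 is the share of respondents choosing one of the top two answers.

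- A person who never saw or skipped the item chose nothing. Putting that person in the denominator means scoring the blank as not agreeing, which is an imputation, and 10.1 and 11.5 rule it out. The denominator is therefore those who answered the item.
- Section 10.2 has no completer condition. Someone who answers at minute 3 and leaves at minute 20 has the primary response and is included. Nothing in 6.5 removes a replaced participant's answers, and 6.4.2 lets the sponsor go on using data collected before consent to disclosure is withdrawn.
- Only people lost in the first few minutes after a watched dose, or who skip the item, are left out. Their number is the safety set minus the number answering.

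**Step 2: the decision rule at n = 400.** The plan gives no cut-off count, expected agreement or dropout rate, so there is no stated figure to reproduce. With x agreeing, p = x/n and z = 1.96, the lower bounds are:

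- Wald: p − z√(p(1−p)/n)
- Wilson: [p + z²/2n − z√(p(1−p)/n + z²/4n²)] / (1 + z²/n)
- Clopper-Pearson (exact): the 0.025 quantile of Beta(x, n−x+1)

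The smallest x with a bound above 50% is 220 (55.0%) for Wald (0.5012) and Wilson (0.5010), and 221 (55.25%) for the exact interval (0.5023).

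**Step 3: how many silent participants would reverse a claim.** Assume 400 answers plus d people dosed without an answer, all counted as not agreeing. This is the harshest case. The table gives the smallest d for which the lower bound of x/(400+d) is 50% or less.

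| Agreeing of 400 | Exact d (share of dosed) | Wilson d | Wald d |
|---|---|---|---|
| 221 (55.25%) | 2 (2/402 = 0.5%) | 3 | 3 |
| 224 (56%) | 8 (8/408 = 2.0%) | 9 | 9 |
| 228 (57%) | 16 (16/416 = 3.8%) | 17 | 17 |
| 232 (58%) | 23 (23/423 = 5.4%) | 24 | 24 |
| 240 (60%) | 39 (39/439 = 8.9%) | 39 | 40 |
| 280 (70%) | 115 (115/515 = 22.3%) | 116 | 116 |

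**Step 4: bounds on the percentage itself.** At 240/400 = 60%, letting none to all of the d agree:

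- d = 8: 240/408 = 58.8% to 248/408 = 60.8%
- d = 20: 240/420 = 57.1% to 260/420 = 61.9%

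**Step 5: the borderline example.** At 221/400 the exact bound is 50.23% and the claim is made. At 221/402 it is 49.97% and the claim fails. At 221/402 Wilson gives 50.09% and Wald 50.11%, so under either of those the claim stands. The reversal needs a result at the cut-off, two early leavers, the exact interval, and a reading of 10.2 that Step 1 does not support.

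**The case for a change.** The best case for a change is that the definition is missing from the study's only primary decision rule and would cost a sentence to supply. Section 10.4 justifies 400 by industry standards and gives no expected agreement rate, so nothing in the documents shows that the result will be far from 55%. Section 10.3 writes a rule for participants who never report cooling in the time-to-cooling analysis, yet none for non-response on the primary item. Section 6.4.2 refers to the schedule of evaluations for data to be collected at discontinuation, and that schedule has no such entry. An all-dosed analysis would let the sponsor speak for everyone who took the tablet.

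Much of this is accurate as description. The term is undefined, no count or reasons are required, and a tidy plan would state the item-level denominator and show numbers dosed and answering. But that wording would only write down what the other sections already imply, and the analysis would come out the same.

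The one proposal that could alter a conclusion is to make the claim also pass with every non-answer scored as disagreement. That adds a second success condition. The study has one arm and no randomized comparison to protect, and a skipped line or an unrelated departure would count against the product. Such a table may be shown as support, but the claim need not depend on it.

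**Conclusion.** No change follows. This is missing detail that an analyst following 10.1, 10.2, 10.3 and 11.5 together would fill in one sensible way: the percentage among those who answered the item, with answers kept from anyone who left afterwards.

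The likely effect is very small. At 60% agreement, 8 unanswered doses would move the all-dosed percentage by at most about 1.2 points (60.0% to 58.8%), and 39 or 40 would be needed to lose the claim. A handful matters only when agreement is within about a point of the 55% cut-off, and then the unnamed interval method can itself decide the matter.

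This rests on two assumptions. The first is that few people are lost between a supervised dose and a questionnaire starting one minute later. The design makes that likely, but no rate is given. The second is that 10.2 is read with the missing-data rules and not in isolation. Heavy early loss would show as a gap between the safety set and the number answering, and the majority statement should then be reported as applying to those who answered.
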